8.2.8. Mean CS Dose on the Day Before Each Visit

For each subject on the day before each scheduled visit, dosage level of Predniso(lo)ne in mg will be summarized using summary statistics by maximum dose level and overall.

For Week 1/Day 1 visit, however, the CS dose is set as the day of, rather than the day before.

If a subject is still enrolled in the study but does not report any CS, then the dosage level is set as 0. If a subject is terminated prior to a visit, then this subject is not included in the calculation for visit.

8.2.9. PDAI, ABSIS, ABQOL and TABQOL scores

Quantitative assessment of patient response and disease progression will be determined using PDAI, ABSIS, ABQOL, and TABQOL scores. The PDAI, ABSIS, ABQOL and TABQOL questionnaires are located in Appendix 15.5.

For each questionnaire, we assume they are taken on the day of visit dates, and use the visit date indicated on the Visit Date CRF as questionnaire date, as the latter are not rigorously QC'ed.

The PDAI questionnaire has two components including activity and damage. The activity component consists of skin, scalp and mucosa parts and the damage component consists of skin and scalp parts. Actual values and change from baseline in PDAI total activity, total damage scores, and total PDAI score will be summarized by maximum dose level and overall, respectively.

The PDAI activity or damage total scores per body part will be calculated as the sum of the scores on that body part as follows. PDAI total activity and total damage scores are calculated and reported by site investigator into EDC.

- PDAI total activity score = Total skin activity + Total scalp activity + Total mucosa activity
- PDAI total damage score = Total skin damage + Total scalp damage

The ABSIS questionnaire has three components, including skin involvement, oral involvement and (oral) severity. The ABSIS scores will be calculated separately for each component. The ABSIS total activity score and total ABSIS score will also be calculated as follows.

- Skin involvement total score = sum of (%BSA * Weighting factor)
- Oral involvement total score = sum score from each oral part
- (Oral) Severity total score = sum of (Level * Factor of discomfort)
- ABSIS total activity score = Skin involvement total score + Oral involvement total score
- Total ABSIS score = Skin involvement total score + Oral involvement total score + Severity total score

Actual values and change from baseline in ABSIS skin involvement total score, ABSIS oral involvement total score and ABSIS total activity score will be summarized for all patients, and for patient subgroups categorized into two groups by a baseline oral involvement total score equal to 0 and >0, and for patient subgroups categorized into two groups by a baseline skin involvement score equal to 0 or >0.

When calculating skin involvement total score, if sum of %BSA = 0, then skin involvement score component is 0. If %BSA > 0, then weighting factor needs to be considered, and if weighting factor is missing in this circumstance, then the skin involvement total score and ABSIS total score are considered missing.

The ABQOL and TABQOL questionnaires both contains 17 questions with numerical scores. The ABQOL and TABQOL scores will be calculated as the sum of scores from each question. Actual values and change from baseline in ABQOL and TABQOL scores will also be summarized overall and by maximum dose level in a table. If individual scores are missing, then total scores as set as missing.

PDAI, ABSIS, ABQOL and TABQOL scores and subscores (for PDAI and ABSIS) by patient and visit will be presented in separate listings.

8.2.10. Simple Nutritional Appetite Questionnaire (SNAQ) score

Simple Nutritional Appetite Questionnaire (SNAQ) contains 4 questions with numerical scores. The SNAQ score will be calculated as the sum of scores from each question. The appetite questionnaire is located in Appendix 15.6. If individual scores are missing, then total scores as set as missing.

Actual values and change from baseline in SNAQ score will be summarized by visit overall and by maximum dose level in a table.

The SNAQ score will be presented in a listing by patient and visit.

8.2.11. Subgroup Analysis

The rates of the primary endpoint will be calculated in selected subgroups:

1. Age (≥ 50 , < 50)
2. Gender
3. Total anti-desmoglein (dsg) antibody (≥ 100 , < 100 units) at baseline.
4. Pemphigus History Type: Newly diagnosed (≤ 6 months from screening) vs. relapsed (> 6 months)
5. Pemphigus Anti-DSG Profile at baseline: PV vs. PF vs. negative anti-dsg profile, where PV is defined as anti-dsg3 positive with anti-dsg1 negative or anti-dsg 3 positive with anti-dsg1 positive. PF=anti-dsg1 positive only vs. neither detectable).
6. Pemphigus Severity: Mild vs. moderate disease severity at baseline (PDAI total activity < 15 vs. ≥ 15). If screening PDAI is not available use Day 1.

9. Safety Analysis

Specific assessments to evaluate treatment safety include the following: the frequency and type of adverse events, clinical laboratory testing, brain MRI (baseline and Day 15 in a subset of patients), vital signs, and symptoms and/or signs of headache, nausea, vomiting or visual disturbances. All analyses of safety will be conducted using the Safety Analysis Population.

For by visit summaries, unscheduled visits, if they exist in the data, will be presented separately after other visits.

9.1. Adverse Events

An AE can be any unfavorable and unintended sign (including an abnormal laboratory finding, for example), symptom, or disease temporally associated with the use of an investigational product, whether or not considered related to the product. All AEs encountered during the study will be reported in detail in the CRF, begins at the time of the first screening/eligibility assessment and ends at the end of the study for each patient. Pre-existing conditions that worsen during a study are to be reported as AEs. Clinically significant changes in physical examination, laboratory safety tests, and vital signs will also be defined as AEs and recorded appropriately. All AEs will be coded using the MedDRA Dictionary (MedDRA, Version 18.0).

Imputation for missing AE onset dates and end dates can be found in Appendix 15.4.

A treatment-emergent AE (TEAE) is defined as an AE that begins on or after the first dose of study drug.

If the AE onset date is missing after imputation and the imputed end date is on or after the first dose of study drug, or if onset date and end date are both missing, then the AE will be classified as a TEAE. If the imputed AE onset date is the same as the first dose of study drug, and AE onset time on or after the first dose of study drug or AE onset time is missing, then the AE will also be classified as a TEAE.

An overall summary of the number and percentage of patients with any TEAE, serious TEAE, study drug-related TEAE, study drug-related serious TEAE, TEAE leading to treatment discontinuation, and AEs leading to death will be provided overall and by maximum dose level.

All AEs will be presented in a listing for the Safety Population.

9.1.1. Incidence of Treatment Emergent Adverse Events

The number and percentage of patients with at least one TEAE and the number of TEAEs will be summarized by SOC and PT, maximum dose level and overall. At each level of SOC or PT, a patient will be counted only once if the patient reported multiple events.

9.1.2. Relationship of Adverse Events to Study Drug

The investigator will provide an assessment of the relationship of the event to the study drug. The possible relationships defined in the protocol are “Not Related” and “Related”.

The TEAEs categorized by SOC and PT will be summarized by maximum dose level and relationship to study drug in a manner similar to that described in Section 9.1.1.

TEAEs that are missing a relationship will be presented in the summary table as “Related” but will be presented in the data listing with a missing relationship.

Related TEAEs will also be presented by SOC and PT.

9.1.3. Intensity Grade of Adverse Event

The NCI CTCAE (version 4.0) will be used for grading AEs.

The TEAEs categorized by SOC and PT will be summarized by maximum dose level and intensity grade in a manner similar to that described in Section 9.1.1. Per each SOC or PT, a patient will be counted only once at the highest grade of intensity.

TEAEs with missing intensity grade will be presented in tables as “Grade 3” but will be presented in the data listing with a missing severity.

9.1.4. Serious Adverse Events

The seriousness of an AE should be assessed by the Investigator independently from the severity of the AE.

The treatment-emergent SAEs categorized by SOC and PT will be summarized by maximum dose level in a manner similar to that described in Section 9.1.1. Treatment-emergent SAEs by relationship to study drug will also be presented in a table. SAE information by patient will be presented in a listing.

9.1.5. Adverse Events Leading to Treatment Discontinuation

The TEAE leading to treatment discontinuation will be summarized by SOC and PT, and maximum dose level in the same way as that described in Section 9.1.1.

All patients who have an AE leading to treatment discontinuation will be presented in a listing.

9.1.6. Death

The TEAE leading to death will be summarized by SOC and PT by SOC and PT, maximum dose level in the same way as that described in Section 9.1.1.

All patients who have an AE with an outcome of death will be presented in a listing.

9.2. Clinical Laboratory Evaluations

Laboratory assessments will be performed at a central laboratory, with the provision for occasional local laboratory testing, if required. The International System of Units (SI units; *Système international d’unités*) will be used and those not reported in SI units will be converted to SI units before analysis.

Summary tables presenting actual values and changes from baseline will be presented for chemistry tests, hematology tests, and coagulation tests overall and by maximum dose level. All relevant clinical laboratory tests will be flagged as Low, Normal, and High according to the normal ranges if applicable. Shift tables will be provided to summarize changes in normality status from baseline to each scheduled post-baseline visit for those tests with normality flags.

The number and percentage of patients for urinalysis tests - will be presented in separate tables. This categorical data will be summarized in shift tables comparing the results at each scheduled post-baseline visit with those at baseline visit.

All lab tests results with normality status will be presented by patient and visit in a listing for the Screening Population.

A special group of clinical laboratory tests which are believed to be the indicators for drug induced liver injury (DILI) will be assessed separately with graphical displays and tabulations. They include:

- ALT (alanine aminotransferase or SGPT)
- AST (aspartate transaminase or SGOT)
- TBL (total bilirubin)
- ALP (alkaline phosphatase)

The test results of the above clinical laboratory tests will be reported in a separate listing and the values outside a number of designated reference ranges will be marked.

Furthermore, scatter plots of the peak TBL divided by the upper limit of the reference range (ULRR) (Y-axis) against peak ALT divided by the ULRR (X-axis), on a log scale, will be created. Lines for Upper limit of the Reference Range (ULRR) for both TBL and ALT, 2xULRR for TBL and 3xULRR for ALT will be presented in the same scatter plot graph. Any patients in the upper right quadrant, which is defined by 2xULRR for TBL and 3xULRR for ALT, would represent cases that were further investigated for potential DILI.

9.3. Vital Sign Measurements

Summary tables presenting observed values and changes from baseline will be provided overall for vital sign measurements, which including systolic blood pressure (mmHg), diastolic blood pressure (mmHg), heart rate (bpm), respiratory rate (bpm), and temperature (°C). All vital sign measurements will be presented in a listing by patient and visit for Safety Population.

Systolic blood pressure values <90 or >140 mmHg or diastolic blood pressure values <60 or >80 mmHg will be flagged as outside the normal range. Resting heart rate <40 or >100 beats per minute will be flagged as abnormal. The number and percentage of patients for each normality category will be summarized overall at each visit.

9.4. Physical Examination

The number and percentage of patients for each body system will be summarized by normality status and overall at each visit.

For the screening visit, the physical examination includes the following body systems: general appearance; skin; eyes, ears, nose, throat; heart; chest/breast; abdomen; neurological; lymph nodes; skeletal; and other. Physical examinations at all other visits will only include: general appearance; abdomen; cardiorespiratory; and other.

Physical examination results for the safety analysis population will be presented in a listing.

For patients from French sites only: if clinically significant headache, nausea, vomiting or visual disturbances have occurred, a full neurological examination, including cranial nerves, will be performed. The neurological symptoms will be documented on AE page. The status of neurological symptoms with relevant AE number, and results of neurological examination will be presented in separate listings.

9.5. Electrocardiogram

Summary tables will be presented for ECG data including ventricular rate (bpm), PR Interval (msec), QRS Duration (msec), QT Interval (msec), QTcF Interval (msec) and QTcB Interval (msec), overall and by maximum dose level for the screening visit.

ECG interpretation at the screening visit will also be summarized overall and by maximum dose level.

If ECG results are collected or interpreted multiple times, the latest one prior to dosing will be used for this summary.

ECG results for the safety analysis population will be presented in a listing.

9.6. Female Reproductive Status and Pregnancy Test Results

The fertility status and method of birth control used for women will be recorded in the CRF at the screening visit. The pregnancy test will be performed for women of childbearing potential only. Pregnancy serum test will be done at the screening visit, urine dip tests will be done at other time points. The reproductive status as well as serum and urine pregnancy test results will be presented in a listing for the safety analysis population.

9.7. Food Intake Status

The food intake status will be recorded in the CRF at each visit. A listing of patient food intake status will be presented for the safety analysis population.

9.8. Brain MRI

Brain MRI with macrocyclic contrast will be conducted on baseline and Day 15 visit for patients from French sites. Date of scan and results will be presented in a listing for the safety analysis population.

10. Pharmacokinetics/ Pharmacodynamics

The analyses of pharmacokinetics and pharmacodynamics (BTK occupancy) will be described and reported outside of the PRN1008-005 study report and attached as appendices.

ITT Analysis Population will be used for TFLs below.

The limit of quantifications for Anti-DSG 1, Anti-DSG 3 and Total Anti-DSG are 14, 9 and one or both of 14 or 9, respectively. Below the threshold is defined as negative, at or above these thresholds is defined as positive.

For Anti-DSG 1 and Anti-DSG 3 data, and a calculated variable of “total DSG” (Anti-DSG 3 and Anti-DSG 1 summed) summary tables presenting actual values and changes from baseline will be presented by visit overall and by maximum dose level. Missing values will not be imputed. This analysis will be performed only using Anti-DSG 1 and Anti-DSG 3 data above the limit of quantification, and for Total Anti-DSG, only use samples where at least one of Anti-DSG 1 or 3 is above the limit of quantification. Two exploratory DSG analyses will be performed:

- 1) CR status (without more than 0.5 mg/kg of CS prior to Week 13) yes/no at the Week 13 visit will be used to compare the change from baseline to Week 5 & 13 in Anti-DSG 1, Anti-DSG 3 data, and total DSG levels.
- 2) CDA status (without more than 0.5 mg/kg of CS and as defined for the primary endpoint) yes/no before Week 5 visit will be used to compare the change from baseline to Week 5 & 13 in Anti-DSG 1, Anti-DSG 3 data, and total DSG levels

All pharmacokinetics and pharmacodynamics data, including plasma concentrations of PRN1008, percentage BTK occupancy in PBMCs, and Anti-DSG 1-3 autoantibody levels (including quantified values below limit of quantification), will be presented in listings.

BTK occupancy data will also be described in a separate report.

11. Interim Analysis

An interim analysis to evaluate safety, and to reevaluate sample size and other aspects of study design, was conducted for this study when 6 patients completed 4 weeks or more of PRN1008 therapy (PRN1008-005 Interim Analysis Report March 20 2017), and again when 26 patients had completed 4 weeks or more of PRN1008 therapy (PRN1008-005 Interim Analysis Report August 15 2018). A further interim analysis will be performed when Part A enrollment and follow up is complete.

12. Safety Monitoring Committee

A Safety Monitoring Committee (SMC) will review the emerging safety data (TEAEs, safety labs), and efficacy, PD, and dose modification data approximately every 3 months within the first 6 months following the first patient enrolled in the study, and then with a frequency determined as appropriate by the SMC. The SMC members will include the Sponsor's Medical Monitor, a Principal Investigator, and a pemphigus clinical expert who is not an investigator in the study. The trial statistician will also participate in safety reviews. Documentation of the patient data reviewed at each meeting, including the individual SMC member's confirmation of data review and the findings and actions of the SMC, will be included in the Trial Master File. SMC findings that impact the safety of patients in this study will be immediately reported to the local Competent Authority (CA) and Ethics Committee (EC).

An SMC Charter outlining the SMC composition and responsibilities will be in place prior to the first scheduled meeting.

13. Changes in the Planned Analysis

In addition to the secondary efficacy endpoints listed in protocol section 11.2, the proportion of patients who are able to achieve CDA/CR at each visit, with or without the need for doses of CS of greater than 0.5 mg/kg will be summarized. Cumulative incidence of patients who ever achieved CDA/CR by each visit will be summarized as secondary efficacy endpoints also.

14. References

PRN1008-005 Interim Analysis Report March 20 2017.

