Only include visits where Anti-DSG are supposed to be measured per protocol, i.e. day 1, week 3, 5, 9, 13, 17, 21 and 25.

Percentage is based on the number of subject with non-missing data for both baseline and post-baseline visit in the parameter of interest.

This analysis will be performed only using Anti-DSG 1 and Anti-DSG 3 data above the limit of quantification, and for Total Anti-DSG, only use samples where at least one of Anti-DSG 1 or 3 is above the limit of quantification at baseline Anti-DSG value is available for each given visit.

Note: Patients are classified into different dose levels according to the maximum dose they received during the 12 week treatment period.

Total Anti-DSG is defined as the sum of Anti-DSG 1 and 3, and is set to missing if either is missing.

Source Data: Listing 16.2.7.3

Table 14.4.2.1

Change from Baseline in Anti-DSG Status by CDA status at Week 5 without Prednis(ol)one >0.5 mg/kg
 ITT Population

CDA BY WEEK 5: YES				
ANTI-DSG PARAMETER TIME POINT Statistics	400mg (N=xx)	500mg (N=xx)	600mg (N=xx)	Total (N=xx)
Anti-DSG 1 (unit)				
BASELINE				
n	xx	xx	xx	xx
MEAN (SD)	xxx.x (xxx.xx)	xxx.x (xxx.xx)	xxx.x (xxx.xx)	xxx.x (xxx.xx)
MEDIAN	xxx.x	xxx.x	xxx.x	xxx.x
MIN, MAX	xxx, xxx	xxx, xxx	xxx, xxx	xxx, xxx
WEEK5 D29				
n	xx	xx	xx	xx
MEAN (SD)	xxx.x (xxx.xx)	xxx.x (xxx.xx)	xxx.x (xxx.xx)	xxx.x (xxx.xx)
MEDIAN	xxx.x	xxx.x	xxx.x	xxx.x
MIN, MAX	xxx, xxx	xxx, xxx	xxx, xxx	xxx, xxx
CHANGE FROM BASELINE AT WEEK5 D29				
n	xx	xx	xx	xx
MEAN (SD)	xxx.x (xxx.xx)	xxx.x (xxx.xx)	xxx.x (xxx.xx)	xxx.x (xxx.xx)
MEDIAN	xxx.x	xxx.x	xxx.x	xxx.x
MIN, MAX	xxx, xxx	xxx, xxx	xxx, xxx	xxx, xxx

Note: Patients are classified into different dose levels according to the maximum dose they received during the 12 week treatment period.
 Control of disease activity (CDA) is defined as the time at which new lesions cease to form and established lesions begin to heal.
 Patients who achieved CDA at the Week 5 visit and had no occurrence of daily prednis(ol)one >0.5 mg/kg before the the first CDA date during the study treatment will be counted as responders.
 Total Anti-DSG is defined as the sum of Anti-DSG 1 and 3, and is set to missing if either is missing.
 Source Data: Listing 16.2.4.1.1, 16.2.7.3

<DIRECTORY PATH>PROGRAM NAME Executed: DMMMMYYYY hh:mm
 Prog Note: repeat for Anti-DSG 3 and Total Anti-DSG.
 PROG NOTE: Repeat for CDA BY WEEK 5 VISIT: No AND OVERALL.

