This analysis will be performed only using Anti-DSG 1 and Anti-DSG 3 data above the limit of quantification, and for Total Anti-DSG, only use samples where at least one of Anti-DSG 1 or 3 is above the limit of quantification at baseline and the Week 5 visit Anti-DSG value is available.

Table 14.4.2.2

Change from Baseline in Anti-DSG Status by CR status at Week 13 without Prednis(ol)one >0.5 mg/kg
 ITT Population

[figure not shown]
CR STATUS BY WEEK 13: YES				
ANTI-DSG PARAMETER	400mg	500mg	600mg	Total
TIME POINT				
Statistics	(N=xx)	(N=xx)	(N=xx)	(N=xx)
Anti-DSG 1 (unit)				
BASELINE				
n	xx	xx	xx	xx
MEAN (SD)	xxx.x (xxx.xx)	xxx.x (xxx.xx)	xxx.x (xxx.xx)	xxx.x (xxx.xx)
MEDIAN	xxx.x	xxx.x	xxx.x	xxx.x
MIN, MAX	xxx, xxx	xxx, xxx	xxx, xxx	xxx, xxx
WEEK13 D85				
N	xx	xx	xx	xx
MEAN (SD)	xxx.x (xxx.xx)	xxx.x (xxx.xx)	xxx.x (xxx.xx)	xxx.x (xxx.xx)
MEDIAN	xxx.x	xxx.x	xxx.x	xxx.x
MIN, MAX	xxx, xxx	xxx, xxx	xxx, xxx	xxx, xxx
CHANGE FROM BASELINE AT WEEK13 D85				
N	xx	xx	xx	xx
MEAN (SD)	xxx.x (xxx.xx)	xxx.x (xxx.xx)	xxx.x (xxx.xx)	xxx.x (xxx.xx)
MEDIAN	xxx.x	xxx.x	xxx.x	xxx.x
MIN, MAX	xxx, xxx	xxx, xxx	xxx, xxx	xxx, xxx

Note: Patients are classified into different dose levels according to the maximum dose they received during the 12 week treatment period.
 Complete response (CR) is defined as the absence of new or established lesions while the patient is receiving minimal or no non-PRN 1008 immunotherapy.
 Patients who achieved CR at the Week 13 visit and had no occurrence of daily prednis(ol)one >0.5 mg/kg on or before the CR date during the study treatment will be counted as responders.
 Total Anti-DSG is defined as the sum of Anti-DSG 1 and 3, and is set to missing if either is missing.
 Source Data: Listing 16.2.4.1.1, 16.2.7.3

<DIRECTORY PATH>PROGRAM NAME Executed: DDMMYYYY hh:mm

Prog Note: repeat for Anti-DSG 3 and Total Anti-DSG. This analysis will be performed only using Anti-DSG 1 and Anti-DSG 3 data above the limit of quantification, and for Total Anti-DSG, only use samples where at least one of Anti-DSG 1 or 3 is above the limit of quantification at baseline and the Week 5 visit Anti-DSG value is available.

Figure 14.2.3.1.1
Kaplan Meier Plots for Time to First Control of Disease Activity (CDA)
ITT Population

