5.4.2.5 Change from Baseline in Simple Nutritional Appetite Questionnaire (SNAQ) score

Simple Nutritional Appetite Questionnaire (SNAQ) contains 4 questions with numerical scores and is assessed at visits specified in the Schedule of assessments (Table 1). The SNAQ score will be calculated as the sum of scores from each question. The SNAQ score ranges from 4 to 20. If individual scores are missing, then the total score is set as missing.

Actual values and change from baseline in SNAQ score at each visit will be summarized by dose level and overall.

The SNAQ score will be presented in a listing by patient and visit.

5.4.2.1 *Change from Baseline and Percent Change from Baseline in Total Anti-DSG, Anti-DSG 1 and Anti-DSG 3*

The Anti-DSG 1 and Anti-DSG 3 results are measured at visits specified in the Schedule of assessments (Table 1). Total Anti-DSG is the sum of Anti-DSG 1 and Anti-DSG3, where at least one of Anti-DSG 1 or 3 is positive per Section 5.1.3, i.e. Anti-DSG 1 \geq 14 and/or Anti-DSG 3 \geq 9.

Actual result, change from baseline and percent change from baseline in Total Anti-DSG, positive Anti-DSG1, i.e. \geq 14, and positive Anti-DSG 3, i.e. \geq 9, at each visit will be summarized by dose level and overall. The same descriptive statistics will be produced by baseline Anti-DSG value (\geq 100 units vs. $<$ 100 unit).

The Total Anti-DSG, Anti-DSG 1 and Anti-DSG 3 values will be presented in a listing by patient and visit.

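### As worded, Anti-DSG 1 and Anti-DSG 3 are summarised at each visit only from values at or above the limit, so a baseline-positive patient who turns negative drops out of that visit's summary

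*SAP*

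**What the plan says.** Change from baseline in anti-desmoglein antibodies is a PD outcome (Protocol 11.3.2).

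**Part A SAP, section 10.** The limits are 14 units for Anti-DSG 1 and 9 for Anti-DSG 3: "Below the threshold is defined as negative, at or above these thresholds is defined as positive". The plan is that "summary tables presenting actual values and changes from baseline will be presented by visit overall and by maximum dose level", with no imputation. The restriction follows: "This analysis will be performed only using Anti-DSG 1 and Anti-DSG 3 data above the limit of quantification". Total Anti-DSG has its own rule: a sample is used if at least one of the two antibodies is above its limit. Two exploratory comparisons of antibody change follow, one by CR status at Week 13 and one by CDA status "yes/no before Week 5 visit will be used to compare the change from baseline". Below-limit results appear in the listings ("including quantified values below limit of quantification").

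**Part A shells.** The notes for Tables 14.4.1.1, 14.4.2.1 and 14.4.2.2 repeat the single-antibody restriction. A reference to baseline then appears in the clause on Total Anti-DSG: "is above the limit of quantification at baseline Anti-DSG value is available for each given visit" for Table 14.4.1.1, and "at baseline and the Week 5 visit Anti-DSG value is available" for the other two.

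**Part B SAP, second section numbered 5.4.2.1.** It plans the actual result, "change from baseline and percent change from baseline in Total Anti-DSG, positive Anti-DSG1" (14 or more) and positive Anti-DSG 3 (9 or more) at each visit, and repeats these by baseline value below 100 versus 100 units or more. The footnotes to Tables B.14.2.2.50.1 and B.14.2.2.51.1 include only values at or above 14 and 9.

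**The concern.** A patient who goes from positive to negative has the most favourable serological course the assay can show. Under the written filter that patient supplies a baseline value but neither a level nor a change at the visit where the result is negative. Inclusion therefore depends on the outcome being summarised, and the baseline row and the visit row describe different patients.

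Three outputs are exposed: the by-visit levels and changes in both parts; the Part B split by baseline value, because patients with low baselines cross the limit most easily; and the Part A comparison by CDA or CR status. In the last, if responders turn negative more often than non-responders, more responders are removed.

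**Working it through.** The documents give no numerical target for this analysis, so there is no figure of the plan's own to reproduce.

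**1. When does the filter apply?** Section 10 restricts the single antibodies by value, with no reference to baseline. Part B ties positivity to each visit. The baseline wording in the Part A shell notes sits in the clause on Total Anti-DSG. It is garbled for Table 14.4.1.1, and under Table 14.4.2.2 it refers to Week 5 although that table reports Week 13. The plain reading for the single antibodies is a filter at each visit.

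**2. What follows without any assumption.**

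- *Level.* Every dropped value is below the limit and every kept value is at or above it. The mean of the kept values therefore exceeds the mean of all values whenever at least one value is dropped.
- *Percent fall.* A follow-up value stays only if it is at least the limit, so the largest fall that can be shown is 1 − limit/baseline. For Anti-DSG 1: 1 − 14/14 = 0%; 1 − 14/21 = 33%; 1 − 14/28 = 50%; 1 − 14/70 = 80%. For Anti-DSG 3: 1 − 9/18 = 50%; 1 − 9/45 = 80%.

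**3. Five invented patients, Anti-DSG 3, limit 9.** Baseline 12, 20, 40, 100, 150; visit 6, 8, 15, 60, 90. The first two are negative at the visit.

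| | All five | Filtered (three) |
|---|---|---|
| Mean visit level | 179/5 = 35.8 | 165/3 = 55.0 |
| Mean change | −143/5 = −28.6 | −125/3 = −41.7 |
| Mean percent change | −252.5/5 = −50.5% | −142.5/3 = −47.5% |

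The filter raises the level, enlarges the absolute fall and shrinks the percent fall.

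**4. Simulation on assumed distributions.** Assumptions, none from the documents: log-normal baseline, median 60 units, log-SD 1.0, baseline-positive patients only; follow-up = baseline × exp(N(ln(1 − fall), SD)), so that percent fall does not depend on baseline; 4 million draws per scenario. Results for limit 14:

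| SD | True fall | Dropped | Mean level, all → kept | Mean change, all → kept | Median percent fall, all → kept |
|---|---|---|---|---|---|
| 0.3 | 30% | 8% | 78 → 84 | −28 → −30 | 30 → 28 |
| 0.3 | 50% | 17% | 55 → 65 | −51 → −58 | 50 → 48 |
| 0.3 | 70% | 36% | 33 → 47 | −73 → −100 | 70 → 68 |
| 0.8 | 30% | 15% | 102 → 118 | −4 → 0 | 30 → 19 |
| 0.8 | 50% | 23% | 73 → 92 | −33 → −34 | 50 → 38 |
| 0.8 | 70% | 38% | 44 → 66 | −62 → −78 | 70 → 58 |

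For limit 9 and a true 50% fall, 10–15% are dropped and the median fall reads 49% to 42.5%.

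*Part B baseline split, limit 14, same true 50% fall in both groups.* Below 100 versus 100 or more reads 47% vs 50% at SD 0.3 (26% vs 0% dropped) and 31% vs 49% at SD 0.8 (33% vs 2% dropped).

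*Part A responder comparison, limit 14.* Suppose responders truly fall 70% and non-responders 30%. The gap in mean change is 73 − 28 ≈ 44 units at SD 0.3 (unrounded 72.7 − 28.4) but reads 100 − 30 = 70. At SD 0.8, 62 − 4 = 58 reads as about 77.

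**5. Does the percent-change direction survive other assumptions?** Let patients with higher baselines fall more (log-slope −0.2 or −0.3 on baseline, centred on a 50% fall at the median). At SD 0.3 the median fall of 51.3% reads about 51.3%, and 51.8% reads 52.3%: no bias, or a slight reversal. At SD 0.5 to 0.8 understatement remains.

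**The case against.** **A baseline-only filter may have been meant.** The Part A shell notes mention baseline. Part B takes its positivity ranges from section 5.1.3, which introduces them for baseline status, and Part B 4.5 plans change for all patients and by baseline value. Under a baseline-only filter nobody who turns negative is lost. This stands as a possibility of intent, not as a reading of the rule: none of these places states it for the single antibodies, and Part B ties positivity to each visit. Two programmers could build different tables.

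**Part B 3.5.3 already plans a count.** It excludes laboratory results beyond a threshold from descriptive statistics and presents the number of patients with such results for each parameter. A reader might therefore infer either that conversions are covered or, overlooking this section, that no count is planned. Neither is supported. Anti-DSG is not among the panels in Part B 5.5.2, the anti-DSG shells have no such row, and a below-threshold count would mix patients negative from the start with those who converted.

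**The distortion may be small.** Beyond the arithmetic in steps 1 and 2, every magnitude rests on assumed distributions. With low variability the median percent fall moves by only 1–3 points. The Part A comparison is labelled exploratory, Part B performs no hypothesis testing, the shells print n, and single values are listed. All of this stands and limits the importance of the point; it does not remove the selection.

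**Conclusion.** The point holds as a defect in the wording of the filter. As written, both SAPs drop a baseline-positive patient from the single-antibody summary of any visit at which the result is negative.

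Two consequences need no distributional assumption: the mean visit level among baseline-positive patients is overstated whenever anyone is dropped, and the percent fall is capped at 1 − limit/baseline. Under the assumed baseline and a true 50% fall, 17–23% of Anti-DSG 1 values and 10–15% of Anti-DSG 3 values would be lost.

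A reader might infer that the filter always makes the antibody response look weaker. The documents do not support that. Mean absolute change can move either way. The Part B percent fall is understated if percent fall does not depend on baseline, but the bias can vanish or reverse if patients with higher baselines fall more. Likewise, the Part A responder comparison is distorted only if conversion differs by response, which is plausible but not shown.

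The primary endpoint is not affected. The sponsor should correct this before the antibody tables are produced or interpreted, but no main conclusion of the trial rests on it.

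**What to change.** In Part A section 10 and Tables 14.4.1.1, 14.4.2.1 and 14.4.2.2, and in the second Part B section 5.4.2.1 and Tables B.14.2.2.49 to B.14.2.2.51:

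- Define each single-antibody set by positivity for that antibody at baseline; for Total Anti-DSG, by at least one antibody positive at baseline.
- Keep every follow-up value in that set. Use the quantified below-limit value where one is reported, and otherwise a substitution stated in advance.
- Report at each visit the number and percent of baseline-positive patients who are negative.
- In Part B, state that this overrides section 3.5.3 for anti-DSG.

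The cost is SAP wording, a changed data filter and one added row per visit. The downside is small: below-limit values are less precise, and Part B does not say whether they are reported as numbers, so the substitution rule may be needed there.
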